(Down-Titration Period). A Down-Titration Visit (DTV) will be performed at the end of the Down-Titration Period, and study drug will be discontinued at the DTV. After 2 weeks free of study drug (Safety Period), study participants will complete the SV.

Brivaracetam (tablet and oral solution) will be administered twice per day in equal doses. The maximum allowed daily dose in EP0132 is 200mg/day (4mg/kg/day). Dose adjustments of BRV and/or concomitant AEDs based on clinical judgment are allowed at any time, 3 days after study start and onwards.

The duration of the study per study participant will be 2 years at minimum, until approval of BRV for the indication of CAE or JAE has been obtained for pediatric participants in their age range, until a managed access program is established as allowed per country-specific requirements in addition to legal and regulatory guidelines, or until the investigational product development in the related indication is stopped by the Sponsor, whichever comes first.

This study will be conducted using a site-based model; all study assessments will be conducted at the study site.

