To investigate long-term efficacy of BRV in pediatric study participants with CAE or JAE	
 Absence seizure freedom based on diary over the Evaluation Period truncated at Month 24 and by each applicable 3-month time interval up to Months 22-24 
Estimand
 
 Population: the study participant population as defined in the protocol-specified inclusion/exclusion criteria reflecting the target patient population. Study participant-level outcome: seizure freedom response on diary over the Evaluation Period truncated at Month 24 and by each applicable 3-month time interval up to Months 22-24. Intercurrent event handling: The intercurrent event of concomitant use of any AED, including benzodiazepines, during each applicable 3-month period is handled in the definition of the participant-level variable implementing a composite strategy in which receiving any concomitant AED, including benzodiazepines, in the 3-month period or during the visit is counted as nonresponse (ie, considered as having absence seizures). The intercurrent event of diary completion during each applicable period is handled in the definition of the participant-level variable implementing a composite strategy in which completing less than 80% of diaries during the 3-month period is counted as nonresponse (ie, considered as having absence seizures). Population-level summary measure: percentage of study participants free from clinical absence seizures.
Secondary objective	Other endpoints
To investigate long-term efficacy of BRV in pediatric study participants with CAE or JAE	
 Consecutive absence seizure freedom in 6-month periods based on EEG up to Month 24 Consecutive absence seizure freedom in 6-month periods based on diary up to Month 24

AED=antiepileptic drug, BRV=brivaracetam, CAE=childhood absence epilepsy, EEG=electroencephalogram, JAE=juvenile absence epilepsy, SAE=serious adverse event, TEAE=treatment-emergent adverse event

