3.3.2 Study periods

For reporting purposes, the Evaluation Period will last from the date of first dose in EP0132 until the FV inclusive, or from the date of first dose in EP0132 until the EDV inclusive for study participants who prematurely discontinue the study. The Evaluation Period may be truncated at the Month 24 YEV for the reporting of the absence seizure freedom based on seizure data (diary and EEG). It is expected that the first dose in EP0132 will be taken in the evening of the EV. For

participants who complete the study at the FV, the Overall Period will include the Evaluation Period only. Otherwise, for participants who are not required to down-titrate as a dose of 1mg/kg/day (50mg/day for study participants with body weight $>50\text{kg}$) is reached at the FV or EDV, the Overall Period will include the Evaluation Period and Safety Period. Otherwise, the Overall Period will include the Evaluation Period, Down-Titration Period and Safety Period.

For study participants who discontinue BRV treatment following the EDV or FV and a dose of $>1\text{mg/kg/day}$ ($>50\text{mg/day}$ for study participants with body weight $\geq 50\text{kg}$) is reached at the EDV or FV respectively, the BRV dose will be reduced by a maximum of half the dose every week for a maximum of 4 weeks until a dose of 1mg/kg/day (50mg/day for study participants with body weight $>50\text{kg}$) is reached (Down-Titration Period). A DTV will be performed at the end of the Down-Titration Period, and study drug will be discontinued at the DTV. Otherwise, for study participants who will discontinue BRV treatment following the EDV or FV and a dose of 1mg/kg/day (50mg/day for study participants with body weight $>50\text{kg}$) is reached at the EDV or FV respectively, down titration will not be applicable.

After 2 weeks free of study drug (Safety Period), study participants will complete the SV.

The definitions of the Evaluation, Down-Titration, Safety Follow-up, and Overall Periods are provided in [Table 3-2](#). Adverse events are assigned to a study period based on the date of onset. All other measurements are assigned based on the date of assessment.

Table 3-2: Definition of study periods

Period	Definition	Algorithmic rule

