3.13.4 Absence seizure freedom based on diary (including dropouts)

The endpoint of absence seizure freedom based on diary will be assessed at 3-month time intervals within the Evaluation Period, as defined in [Table 3-3](#), and over the entire Evaluation Period. The Evaluation Period may include any additional diary entries collected from the end of the Months 22 to 24 period up to the Month 24 YEV where the Evaluation Period is truncated for participants who reach the Month 24 YEV.

In each 3-month period (or Evaluation Period), a study participant is defined as absence seizure free if they meet all the following criteria:

1. The study participant completed their seizure diary on at least 80% of days within the relevant period. Seizure diary is defined as completed if “Diary completed” is answered “Yes” for each applicable day in the period. If “Diary completed” is answered “No” or the diary record is missing it will be defined as not completed for that day.
2. No absence seizures are reported in the seizure diaries in the relevant period
3. No concomitant use of any AEDs, including benzodiazepines during the relevant period

Specific algorithmic rules for each of the above criteria are defined as follows:

Criterion 1: Seizure diary data is reported on the Seizure Classification eCRF for at least 80% of the days within the relevant period

Criterion 2: No diary records on the Seizure Classification eCRF within the relevant period are reported with answer “Yes” to the question “Did Any Absence Seizures occur?”

Criterion 3: No records of any concomitant AED, including benzodiazepines, usage on the Concomitant Medications eCRF within the relevant period

Note that Criterion 2 and 3 will only be assessed if Criterion 1 is met. In each 3-month period (or Evaluation Period), if the study participant does not meet all the criteria for absence seizure freedom they will be regarded as not absence seizure free.

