If a study participant discontinues the study during a 3-month period then Criterion 1 will be checked based on the full 3-month period and if met, the participant will be assessed for absence seizure freedom in the period of discontinuation. If Criterion 1 is not met, absence seizure freedom status will be imputed as not absence seizure free for the period of discontinuation and all subsequent 3-month periods, ending at Months 22 to 24. Study participants who discontinue the study early will still be included in the analysis conducted on the Evaluation Period.

If a study participant has a FV during a 3-month period then Criterion 1 will be checked based on the full 3-month period and if met, the participant will be assessed for absence seizure freedom in the period of the FV. If Criterion 1 is not met, the participant will not be included in the summary for that period and all subsequent 3-month periods, ending at Months 22 to 24. Study participants who have a FV prior to the scheduled Month 24 YEV will still be included in the analysis conducted on the Evaluation Period.

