3.13.5 Absence seizure freedom based on diary (excluding dropouts)

The endpoint of absence seizure freedom based on diary will be assessed at 3-month time intervals within the Evaluation Period, as defined in [Table 3-3](#), and over the entire Evaluation Period. The Evaluation Period may include any additional diary entries collected from the end of the 3-month Months 22 to 24 period up to the Month 24 YEV where the Evaluation Period is truncated for participants who reach the Month 24 YEV.

The derivation will be the same as [Section 3.13.4](#) apart from if a study participant discontinues or completes the study during a 3-month period then Criterion 1 will be checked and if met, the participant will be assessed for absence seizure freedom in the period of discontinuation. If they do not meet Criterion 1 during the period of study discontinuation the study participant will not be included in the analysis for that period. Additionally, they will not be included in the analysis of any period subsequent to that of study discontinuation or completion. If a study participant discontinues the study at any time before the scheduled Month 24 YEV, they will not be included in the analysis conducted on the Evaluation Period. However, if a study participant has a FV prior to the scheduled Month 24 YEV, they will be included in the analysis conducted on the Evaluation Period.

3.13.6 Absence seizure freedom based on diary with modified criterion based on seizure diary completion (including dropouts)

The endpoint of absence seizure freedom based on diary with modified criterion based on seizure diary completion (including dropouts) will be derived in the same way as the endpoint defined in [Section 3.13.4](#), however Criterion 1 will be updated to require a minimum of 50% of days of seizure diary completion within the relevant period.

3.13.7 Absence seizure freedom based on diary with modified criterion based on seizure diary completion (excluding dropouts)

The endpoint of absence seizure freedom based on diary with modified criterion based on seizure diary completion (excluding dropouts) will be assessed at 3-month time intervals within the Evaluation Period, as defined in [Table 3-3](#), and over the entire Evaluation Period. The Evaluation Period may include any additional diary entries collected from the end of the Months 22 to 24 period up to the Month 24 YEV where the Evaluation Period is truncated for participants who reach the Month 24 YEV.

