8.1.3 Absence seizure freedom based on diary (including dropouts)

The number and percentage of study participants who are absence seizure free based on diary will be summarized at 3-month time intervals within the Evaluation Period, as defined in [Table 3-3](#), and over the entire Evaluation Period truncated at the scheduled Month 24 YEV for participants who continue in the study beyond 2 years. The latter will additionally include any diary entries collected from the end of Months 22 to 24 up to the Month 24 YEV. The derivation of absence seizure freedom based on diary is specified in [Section 3.13.4](#).

Study participants who discontinue during or prior to each 3-month period and do not meet Criterion 1 are imputed as not absence seizure free for the period of discontinuation and all subsequent 3-month periods, ending at Months 22 to 24. These participants will be separately summarized as a sub-category of not absence seizure free in the summaries.

Similarly, study participants who discontinue during the Evaluation Period and do not meet Criterion 1 are imputed as not absence seizure free for the Evaluation Period; these participants will be summarized in a sub-category as described above.

The number and percentage of study participants who met each individual criterion will also be summarized. Percentages for absence seizure free, not absence seizure free and Criterion 1 will be based on the number of participants in the SS as the denominator. Percentages for criteria 2 and 3 will be based on the number of participants in the SS who met Criterion 1 at each visit.

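### The Evaluation Period diary result pools participants assessed only up to an early Final Visit with those followed to Month 24, and does not show the two apart

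*SAP*

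**What the plan says.** SAP 2.2.2 (Table 2-2) defines the secondary endpoint as "Absence seizure freedom based on diary over the Evaluation Period truncated at Month 24", alongside the 3-month intervals. SAP 3.3.2 makes that period specific to each participant: "the Evaluation Period will last from the date of first dose in EP0132 until the FV inclusive". Section 8.1.3 applies the cut "over the entire Evaluation Period truncated at the scheduled Month 24 YEV for participants who continue in the study beyond 2 years".

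SAP 3.13.4 sets three criteria: "The study participant completed their seizure diary on at least 80% of days within the relevant period"; "No absence seizures are reported in the seizure diaries in the relevant period"; and no concomitant AED in that period.

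For an FV before Month 24, the including-dropouts version has this rule for its whole-period result: "Study participants who have a FV prior to the scheduled Month 24 YEV will still be included in the analysis". The excluding-dropouts version (3.13.5) agrees: "if a study participant has a FV prior to the scheduled Month 24 YEV, they will be included in the analysis". Sections 3.13.6 and 3.13.7 carry the rule into the sensitivity analyses with 50% diary completion. Section 3.13.9 defines consecutive diary freedom over the entire Evaluation Period as well, and assesses an FV participant who meets Criterion 1 in the relevant period.

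Protocol 4.1 gives a two-year minimum but lists it with approval, managed access and a development stop: "or until the investigational product development in the related indication is stopped by the Sponsor, whichever comes first". It also assigns an FV, not an Early Discontinuation Visit (EDV), to participants who move to another BRV study, an access program or commercial drug. Table 1-2, footnote b, allows for an FV before Month 24 on transfer to another BRV study.

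**The concern.** Participants with unequal time at risk share one percentage. Someone who moves to an access program at Month 6 with a clean diary counts as a success equal to someone free for 24 months, although being free of seizures and AED use is easier over a shorter window.

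Other rows treat early FVs differently. The by-visit EEG rows (3.13.2, 3.13.3) drop these participants after the FV. The 3-month diary rows check Criterion 1 against the full interval and leave the participant out if it fails. The cumulative diary row (3.13.9) removes still-free participants from later periods. In the Evaluation Period row a short window stands for the whole, and no sub-category shows how many successes rest on one. Section 8.1.3 does give a sub-category for discontinued participants imputed as not free.

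At stake is the reading of the whole-period diary result under the long-term efficacy objective: part of the percentage could reflect when administrative exits occur.

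**Working it through.** There is no planned rate to reproduce. The study is descriptive, and the figure of about 140 is a rollover expectation (SAP 2.4).

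**Direction.** Freedom from seizures and AED use over a shorter window is never rarer than over 24 months, so for these criteria the effect on a 24-month reading is upward or zero. Criterion 1 scales with own time: 0.80 × 180 = 144 diary days for an FV at Day 180, 0.80 × 365 = 292 at Day 365, and 0.80 × 731 = 584.8, so 585, at the Month 24 visit. Criterion 1 is not monotone in time. A participant could fail 80% early and pass over 24 months, which is a small effect the other way.

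**Size (assumptions, not in the documents).** Accrual is uniform over A months. One administrative end date falls L months after the last entry. The probability q of staying free in each 3-month period is constant and unrelated to entry date. Nobody discontinues, and diary completion is met.

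- Share short of Month 24: f = (24 − L)/A.
- Their FVs are spread evenly over Months L to 24.
- True 24-month freedom: q^8.
- Mean freedom to FV in the short group: m = (q^(L/3) − q^8) / [((24 − L)/3) × (−ln q)].
- Row shown: (1 − f) × q^8 + f × m.

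Worked case, A = 36, L = 12, q = 0.85: f = 12/36 = 33.3%; q^8 = 0.2725; q^4 = 0.5220; −ln q = 0.1625; m = (0.5220 − 0.2725)/(4 × 0.1625) = 0.384. Row = 0.667 × 0.2725 + 0.333 × 0.384 = 0.310.

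| A | L | q | f | true 24-month | m | row | excess |
|---|---|---|---|---|---|---|---|
| 36 | 12 | 0.85 | 33.3% | 27.2% | 38.4% | 31.0% | +3.7 |
| 36 | 12 | 0.90 | 33.3% | 43.0% | 53.5% | 46.5% | +3.5 |
| 36 | 18 | 0.85 | 16.7% | 27.2% | 32.2% | 28.1% | +0.8 |
| 48 | 12 | 0.85 | 25.0% | 27.2% | 38.4% | 30.0% | +2.8 |

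In the first case the excess is 0.037 × 140, about 5 participants.

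**Wider range.** Exits through transfer or access programs need not follow one end date. Let a share f have an FV at a fixed Month t, with 24-month freedom S and constant hazard. The excess is then f × (S^(t/24) − S). With S = 40%, f = 20% and t = 12 this is 0.20 × (0.632 − 0.40) = +4.6 points. Over S of 20% to 60%, f of 5% to 40% and t of 6 to 18 it runs from +0.4 to +18.7 points. It is zero if f = 0 or if nobody would have failed after the FV.

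**The case against.** The strongest reply is that the row estimates what it defines. The protocol endpoint is freedom over the evaluation period, which is a participant-specific window, and the Month 24 wording is a cap for those who stay longer. A reader might infer that the SAP presents this as a 24-month rate and so overstates it. The documents do not support that: the bias exists only when the row is read as a fixed 24-month figure. This part of the objection stands.

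The design also points to two years. Protocol 6.1 expects at least two years of treatment, Table 1-1 puts the FV at Month 24, and Table 1-2 has it at Month 24 or later. Early FVs may be few. That limits the likely size but does not remove the point, because the SAP writes explicit rules for FVs before Month 24.

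A reader might pair the 33% share with a much earlier exit, such as Month 9. That cannot happen under the accrual scenario used here, where everyone has at least 12 months of follow-up.

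Nor is this the only long-term diary result. The cumulative consecutive analysis (3.13.9, 8.1.6) runs to Months 19 to 24 and drops still-free early-FV participants, although it ignores AED use. Disposition tables (5.1.1) will show visit attendance and who starts and completes each 3-month period, but they do not link this to seizure freedom. Distortion between countries is not a live issue, since SAP 3.9 rules out assessing outcomes by country.

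Finally, the sponsor might intend Criterion 1 to be checked against the full 24 months. An FV at Day 365 could then supply at most 365/731 = 49.9% of days and would fail both the 80% and 50% versions, which reverses the bias. Table 3-2 does not support that reading, but the text does not exclude it expressly.

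**Conclusion.** The point holds as one of unequal follow-up and labelling. The Evaluation Period diary row mixes short-window successes with 24-month ones and gives no means of telling them apart. Read as 24-month freedom, it is biased upward on the seizure and AED criteria, or not at all. Under the single-end-date scenarios the excess is about 1 to 4 points. Other assumed exit patterns give less or considerably more. All of these rest on assumed accrual, exit timing and recurrence, and the number of participants affected cannot be known from the documents.

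A reader might also conclude that the percentage should give way to a Kaplan-Meier estimate. The documents do not support that as the main analysis. The stated summary measure is a percentage. Diary completion below 80% counts as nonresponse and has no event date over a whole period. Treating every discontinuation as an event would depart from 8.1.3, which imputes nonresponse for the Evaluation Period only when Criterion 1 fails.

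**What to change.** Keep the planned percentage, and make these changes:

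- In SAP 8.1.3, 8.1.4, 8.1.6 and 8.1.7, show the Evaluation Period result separately for participants with an FV before Month 24 and for those followed to the Month 24 visit, with the number and follow-up time of each. In the including-dropouts tables keep early discontinuers as their own group, so that the groups add up to the Safety Set.
- In 3.13.4 to 3.13.7 and 3.13.9, state that Criterion 1 for an early-FV participant is checked from first dose to FV.
- Do not describe the pooled row as 24-month seizure freedom in the tables or the report.
- Optionally, add a Kaplan-Meier estimate at Month 24 with censoring at the FV, as supportive only, stating how diary completion below 80% and early discontinuation are handled.

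The cost is SAP wording and one extra split in each affected output, from diary data already collected. The subgroups will be smaller, more so by CAE and JAE, and the long-term figure may look less favourable.

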3.13.5 Absence seizure freedom based on diary (excluding dropouts)

The endpoint of absence seizure freedom based on diary will be assessed at 3-month time intervals within the Evaluation Period, as defined in [Table 3-3](#), and over the entire Evaluation Period. The Evaluation Period may include any additional diary entries collected from the end of the 3-month Months 22 to 24 period up to the Month 24 YEV where the Evaluation Period is truncated for participants who reach the Month 24 YEV.

The derivation will be the same as [Section 3.13.4](#) apart from if a study participant discontinues or completes the study during a 3-month period then Criterion 1 will be checked and if met, the participant will be assessed for absence seizure freedom in the period of discontinuation. If they do not meet Criterion 1 during the period of study discontinuation the study participant will not be included in the analysis for that period. Additionally, they will not be included in the analysis of any period subsequent to that of study discontinuation or completion. If a study participant discontinues the study at any time before the scheduled Month 24 YEV, they will not be included in the analysis conducted on the Evaluation Period. However, if a study participant has a FV prior to the scheduled Month 24 YEV, they will be included in the analysis conducted on the Evaluation Period.

3.13.6 Absence seizure freedom based on diary with modified criterion based on seizure diary completion (including dropouts)

The endpoint of absence seizure freedom based on diary with modified criterion based on seizure diary completion (including dropouts) will be derived in the same way as the endpoint defined in [Section 3.13.4](#), however Criterion 1 will be updated to require a minimum of 50% of days of seizure diary completion within the relevant period.

3.13.7 Absence seizure freedom based on diary with modified criterion based on seizure diary completion (excluding dropouts)

The endpoint of absence seizure freedom based on diary with modified criterion based on seizure diary completion (excluding dropouts) will be assessed at 3-month time intervals within the Evaluation Period, as defined in [Table 3-3](#), and over the entire Evaluation Period. The Evaluation Period may include any additional diary entries collected from the end of the Months 22 to 24 period up to the Month 24 YEV where the Evaluation Period is truncated for participants who reach the Month 24 YEV.

The derivation will be the same as [Section 3.13.4](#), however Criterion 1 will be updated to require a minimum of 50% of days of seizure diary completion within the relevant period. If a study participant discontinues or completes the study during a 3-month period then Criterion 1 will be checked and if met, the participant will be assessed for absence seizure freedom in the period of discontinuation. If they do not meet Criterion 1 during the period of study discontinuation the study participant will not be included in the analysis for that period. Additionally, they will not be included in the analysis of any period subsequent to that of study discontinuation or completion. If a study participant discontinues the study at any time before the scheduled Month 24 YEV, they will not be included in the analysis conducted on the Evaluation Period. However, if a study participant has a FV prior to the Month 24 YEV, they will be included in the analysis conducted on the Evaluation Period.

